4.2 Participant Recruitment, Eligibility Criteria and Study Procedures

Patients will be recruited at the respective outpatient clinics. At the usual care clinic appointments, patients have their demographics and baseline data of blood pressure, blood sugar, basic blood profiles, asthma control and review of their disease management collected by consultants/researchers. Patients who meet the study criteria will then be instructed to see pharmacists/researchers at outpatient pharmacy to refill their medications. The pharmacists/researchers will screen patients' inclusion and exclusion criteria for this study and will explain that they may or may not be selected for the study and if they agree, proceed to provide written informed consent. The adherence data from the screening will be collected to gauge the general adherence rate in these group of patients. An independent researcher, who is not involved in the intervention and control groups, will use the random number function in Excel to generate randomisation sequences. The random numbers will be placed in opaque envelopes, which subsequently will be opened by pharmacists/researchers at the outpatient pharmacies. Participants and pharmacists/researchers are unblinded to group assignment and are aware of the intervention, but the study hypotheses are not disclosed to the participants. The assessor and statisticians are blinded to participant allocation. The study will be evaluating usual care compared with usual care plus pharmacist-driven patient-specific adherence interventions - CareAide® medication adherence digital application. Usual care provided by these hospitals comprises clinic appointments every 3 to 6 months.

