4.2.2 Control group

- Control group will not be asked to download any digital applications but only receive the usual care by the hospitals.

4.3 Patients' inclusion and exclusion criteria are as follow:

4.3.1 Inclusion criteria:

- Age: 18 years and above
- Diagnosed with selected non-communicable diseases (NCDs): hypertension, diabetes mellitus, heart failure or asthma for at least 6 months
- Prescription generated from one of the following specialty clinics: Medical, Cardiology, Diabetes Mellitus or Asthma clinics
- Medications are prescribed in previous 3 months and refill at the point of recruitment
- Morisky Medication Adherence Scale (MMAS) score < 6
- More than three medications daily or two medications with multiple dosing intervals.
- One or more hospital admissions in the prior 24 months
- Understand and able to command in English and own a smartphone

4.3.2 Exclusion criteria:

- Medications prescribed from other institution providers
- Existing mobile health app or medication reminder app user
- Pregnant
- Cognitively impaired
- Prisoners
- Bed-bound
- Severe diseases/comorbidities – terminal cancer, psychiatry, etc

4.3.3 Withdrawal criteria:

Participants can choose to withdraw at any time for any reason, specified or unspecified, and without prejudice to their care. Participants may be withdrawn if the investigator feels that it is not for the participants' best interest to continue. The following is a list of possible reasons for study intervention discontinuation:

- Screening failure

- Participant withdrawal of consent
- Participant is not compliant with study procedures
- Protocol violation requiring discontinuation
- Lost to follow-up
- Request from sponsor for early termination of study
- Participant death

Withdrawn participants will not be replaced. It will be documented whether or not each subject completes the clinical study. If the Investigator becomes aware of any serious, related adverse events after the subject completes or withdraws from the study, they will be recorded in the source documents and on the Case Report Form (CRF). The Investigator will contact participants who are lost to follow-up. Contacts attempts with such subjects will be documented in the participant's records (e.g., times and dates of attempted phone contact, receipt for mailing a registered letter, etc.).

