4.4.1.1 Primary outcome

Medication adherence: CareAide® effectiveness is measured with a medication adherence tool at baseline and follow-up time periods at 3 months and 6 months using Morisky Medication Adherence Scale-8 (MMAS-8) and proportion of days covered (PDC). The primary outcome of the study is medication adherence, which is assessed using the 8-item Morisky Medication Adherence Scale (MMAS-8) and the Proportion of Days Covered (PDC) method. Measurements are taken at baseline and at two additional time points, with a 3-month interval following the intervention. MMAS-8 is a licensed validated questionnaire to assess medication adherence, where a higher score represents higher medication adherence and vice versa. Comprising of 8 items, the score ranges from 0 to 8, where a higher score represents a higher medication adherence. The internal consistency (Cronbach's alpha) of MMAS-8 is 0.83 along with a sensitivity of 93% and a specificity of 57%. The PDC method utilises pharmacy refill records (Raebel et al., 2013). The PDC can be calculated as below (Hess et al., 2006; Raebel et al., 2013; Pednekar et al., 2019):

$Nm/Nd \times 100\%$

Where N_m denotes the number of days covered by the medication while N_d meant the number of days in the study period. The patients are considered to be adherent if their PDC scores are ≥ 0.8 or 80% (Karve et al., 2009). The prescription refill data was extracted from outpatient/hospital database.

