4.5 Sample Size

The primary outcome for this study is to assess medication adherence of patient after using mobile health application. Therefore, sample size for this randomized controlled trial is calculated using the continuous outcome formula below (Charan & Biswas, 2013; Wittes, 2002):

$$n_i = \frac{2(Z_{\alpha/2} + Z_{\beta})^2 P (1 - P)}{(P_1 - P_2)^2}$$

n_i = sample size required for each group ($i = 1,2$)

$Z_{\alpha/2}$ = Assumed type I error: α equal to 5%, then $Z_{0.05/2} = Z_{0.025} = 1.96$ (From Z table)

Z_{β} = Assumed power of 80% $Z_{\beta}=0.84$

$P_1 - P_2$ = Effect Size= Difference in the proportion of events in two groups

P = Total prevalence

Total Sample size needed: 388 per group

Note: Based on few past studies reported for non-adherence rate for patients in Malaysia is within 46.6% to 56% (Ting et al., 2019). Therefore, assumption of prevalence of chronic disease is 70%

of the adult and adherence rate of 50% is made. A systematic review showed that mobile app able to improve adherence by 7% to 40% (Pérez-Jover et al., 2019). Medication non-adherence rate of 50% is expected in control group and 40% is expected in intervention group. For a 10% absolute difference in medication non-adherence rate between control and intervention group, 388 patients per arm should be recruited in the study assuming a type I error of 5% and power of 80%.

N (number to enrol) * (1-% drop out) = desired sample size

Therefore N (number to enrol) = desired sample size / (1- % drop out)

$N = 388 / 0.80 = 485$ per group

Based on a systemic review published by Wood and colleagues found out there is a possibility of 20% loss of follow-up, drop out and those who are unable to meet the inclusion criteria (Wood et al., 2004). Therefore, a minimum sample size of 970 is needed in this study, with the number of 485 in each arm.

The sample size obtained from the primary outcome is too large and which might need to spend more time and manpower. Hence, the sample size calculation is repeated with the use of secondary outcome which is cost-effectiveness economic evaluation of the study. Glick (2011) formula is applied for the calculation of sample size as it incorporates all important economic evaluation informations such as difference in treatment costs and effects and willingness to pay threshold in a single formula.

$$n_i = \frac{2 \left(Z_{\alpha/2} + Z_{\beta} \right)^2 \left(Sd_c^2 + (W^2 Sd_Q^2) - (2 W p Sd_c Sd_Q) \right)}{(W\Delta Q - \Delta C)^2}$$

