4.6 Data Analyses

Intention to treat (ITT) analysis will be applied to evaluate the results to avoid any bias. The data analysis will be using the SPSS version 27. Data will be coded and analysed. Descriptive or categorical data will be expressed as mean \pm standard deviation (SD) unless otherwise stated. Student t-test will be used for analysis of normally distributed or continuous variables. Mann-Whitney test will be used for non-normally distributed data. Categorical data will be analysed using Chi-square or Fischer's exact test. A value of $P < 0.05$ is considered statistically significant.

The prevalence of medication compliant is quantified at 3 months and 6 months follow-up. Independent t-test or Mann-Whitney test will be used to compare MMAS score rankings between the intervention and control groups. Chi-Square test of independence will be used to determine the difference in number of patients with medication adherence between the intervention and control groups at 3 months and 6 months follow-up. Ordinal logistic regression, with the MMAS adherence score ranking, will be used to examine the association between intervention and control groups.

For the perception and satisfaction towards the app, the frequency and percentage of respondents in each category (strongly disagree to strongly agree) will be calculated. The median of each statement will then be calculated to give an overview of perception and satisfaction towards the CareAide® app. Chi-square, Mann-Whitney U, Kruskal Wallis, Chi-square tests and logistic regression will be used where appropriate. The open-ended question will be analysed using thematic analysis as proposed by Braun and Clarke (2012). Codes will be assigned to the data to describe the content. After the coding is completed, themes will be generated, reviewed, and named. Linear regression analysis will be conducted to determine the independent predictors of HRQoL.

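### Section 4.6 leaves the measured baseline MMAS-8 score out of the between-arm adherence analyses, a modest and avoidable loss of precision

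*Combined protocol and SAP*

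**What the plan says.** Section 4.4.1.1 makes adherence, by MMAS-8 and by proportion of days covered (PDC), the primary outcome: "Measurements are taken at baseline and at two additional time points, with a 3-month interval following the intervention". Section 4.3.1 admits only patients with "Morisky Medication Adherence Scale (MMAS) score < 6", and section 4.2 adds: "The adherence data from the screening will be collected to gauge the general adherence rate in these group of patients". A pre-intervention score therefore exists for every enrolled patient.

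Section 4.6 uses that score in no between-arm comparison:

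- MMAS: "Independent t-test or Mann-Whitney test will be used to compare MMAS score rankings between the intervention and control groups".
- Adherent yes or no: a chi-square test at 3 and at 6 months.
- The one model for adherence: "Ordinal logistic regression, with the MMAS adherence score ranking, will be used to examine the association between intervention and control groups".

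No baseline value, change score or covariate is named for any of them. The other regressions in section 4.6 concern predictors of quality of life and the app survey.

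Section 4.5 first sizes the trial on adherence: "Therefore, a minimum sample size of 970 is needed in this study, with the number of 485 in each arm". It then judges this too large and adopts 200 patients from a cost-effectiveness calculation.

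**The concern.** When an outcome is also measured at baseline, a comparison of follow-up values alone leaves in the error term whatever variation the baseline value could explain. A model with the baseline value as covariate removes it at no cost in patients. That matters more than usual here, because the sample was limited for reasons of time and manpower to about a fifth of what the adherence calculation asked for. What is at stake is the width of the confidence interval for the primary outcome. The validity of the comparison is not in question.

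**Working it through.** **The plan's own figure.** With 50% and 40% non-adherence, mean P = 0.45, z values 1.96 and 0.84: n = 2 × 2.8² × 0.45 × 0.55 / 0.10² = 388.08, which is the plan's 388 per arm. Then 388 / 0.80 = 485 per arm, 970 in total. This reproduces.

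**Evaluable patients at the adopted size.** 200 × 0.8 / 2 = 80 per arm.

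**MMAS-8 score.** ANCOVA multiplies the variance by (1 − r²), where r is the baseline-to-follow-up correlation among enrolled patients. So 80 patients work like 80 / (1 − r²), and the interval shrinks by the factor √(1 − r²). The detectable difference with 80% power, unadjusted, is 2.8 × √(2/80) = 0.443 SD. The documents give no r, so each value below is an assumption.

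| r among enrolled | 80 works like | Interval factor | Detectable difference |
|---|---|---|---|
| 0 (unadjusted) | 80 | 1.000 | 0.44 SD |
| 0.30 | 87.9 | 0.954 | 0.42 SD |
| 0.33 | 89.8 | 0.944 | 0.42 SD |
| 0.36 | 91.9 | 0.933 | 0.41 SD |
| 0.50 | 106.7 | 0.866 | 0.38 SD |

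**Which r is plausible for MMAS.** Keeping only scores below 6 narrows the baseline range and weakens the correlation. For a normal score cut at its mean, the retained variance is 1 − 2/π = 0.363 of the original. With r = 0.5 before selection, the correlation afterwards is 0.5 × √0.363 / √(0.75 + 0.25 × 0.363) = 0.301 / 0.917 = 0.33. Simulations with a score limited to 0-8 (mean 5.5-6, SD 1.5-2, all assumed) gave 0.33-0.36. So 0.33-0.36 is the better central case: 80 works like about 90-92, and the interval is about 6-7% narrower. To have 0.5 among enrolled patients, r would need to be about 0.7 before selection (simulation: 0.7 falls to 0.51). If r is only 0.3 before selection it falls to about 0.19, and 80 works like 80 / (1 − 0.19²) = 83.

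**Does ANCOVA behave on a bounded score?** In 20,000 simulated trials (0-8 score, baseline below 6, mean 6, SD 2, r = 0.5 before selection), type I error was 0.052. Power for a 0.8-point shift was 0.81, against 0.77 for the t-test.

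**Binary adherence, 50% against 40%, 80 per arm.** Null standard error √(2 × 0.45 × 0.55 / 80) = 0.0787; alternative √((0.25 + 0.24) / 80) = 0.0783. Then (0.10 − 1.96 × 0.0787) / 0.0783 = −0.69, which gives power 0.244. Simulated logistic regression with a continuous baseline (20,000 trials each, Wald test) gave 0.260 for r = 0.3 and 0.282 for r = 0.5. To reach 80% power by adjustment alone, r² would have to be about 1 − 80/388 = 0.79, that is r of about 0.89.

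**The case against.** **The tests are valid and the gain is small.** Both are true. Randomisation protects the unadjusted comparison, so a reader who infers bias goes too far. A gain of about ten patients per arm is modest, but it costs nothing.

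**The ordinal regression could carry covariates.** It could, and silence is not a decision against adjustment. But section 4.6 names only the groups, and covariates chosen after the data are seen invite selective reporting. Stating them now removes that risk.

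**The real problem is the sample size.** This stands. A reader might infer that adjustment would rescue the adherence comparison after the cut from 970 to 200. At 24% rising to 26-28%, it does not.

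**Adjusted logistic regression changes the measure.** This also stands. Section 4.5 is framed as a difference in proportions, while a logistic coefficient is a conditional odds ratio. The fix below therefore reports a marginal risk difference.

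**PDC is less settled.** Section 4.6 never names PDC. Section 4.4.1.1 says its denominator "meant the number of days in the study period", which leaves the baseline window undefined. Entry also requires "Medications are prescribed in previous 3 months and refill at the point of recruitment", which may narrow baseline PDC. The gain is secure only for MMAS-8.

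**A reader might infer that baseline adjustment would shrink the economic sample size.** The documents do not support that.

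- Sections 4.4.1.2 and 4.6 state a baseline only for patient-reported resource use, not for direct costs or EQ-5D-5L. The flow chart, not shown in the text available, may settle this.
- The plan's 75 per arm arises only if the 30% cost difference is an added cost. The net-benefit variance is 1000² + 284.7² − 2 × 28,470 × 0.1 × 1000 × 0.01 = 1,024,114. Then 15.68 × 1,024,114 / (284.7 − 749.7)² = 74.3; as a saving, the denominator (284.7 + 749.7)² gives about 15.
- How much QALY adjustment would help depends on the assumed QALY SD of 0.01.

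**Conclusion.** The point holds as a modest loss of precision. Section 4.6 names no baseline term, although a baseline MMAS-8 score is available for every enrolled patient. On an assumed correlation of 0.5 before selection, the entry rule leaves about 0.33-0.36, and 80 evaluable per arm would work like about 90-92. Over an assumed range of 0.3 to 0.5 among enrolled patients the figure is 88 to 107, and the upper end is unlikely for MMAS because of the entry rule. The size rests wholly on correlations that the documents do not give, and on 20% attrition from 200. For the binary contrast the gain is only two to four percentage points of power. No reduction in the economic sample size is claimed.

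**What to change.** Amend section 4.6 as follows.

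1. **MMAS-8 score at 3 and 6 months.** Make ANCOVA on arm and continuous baseline MMAS-8 the main comparison, with robust or bootstrap standard errors if residuals are skewed. Specify the score recorded before the allocation envelope is opened.
2. **Ordinal logistic regression.** Add continuous baseline MMAS-8. Do not use a baseline category: entry requires a score below 6, so with any cut at 6 or above the category is the same for everyone.
3. **Binary adherence.** Fit logistic regression on arm and continuous baseline MMAS-8. Report the standardised (marginal) adjusted risk difference, so that the planned difference in proportions remains the measure. Show the chi-square result and crude difference alongside.
4. **PDC.** Treat it the same way once the look-back window for baseline PDC is stated.
5. **Costs and QALYs.** State whether direct costs and EQ-5D-5L are collected at baseline. Where they are, adjust each for its baseline value within every bootstrap replicate before forming the ICER and acceptability curve.

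For MMAS-8 this is a free improvement: a few lines of text, standard models in the planned software, and no new data or patients. The standardised risk difference needs a little extra programming. PDC depends on a definition still to be written, and the economic step on confirmed baseline collection.

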
$n_i =$ sample size required for each group ($i = 1,2$)

$Z_{\alpha/2} =$ Assumed type I error: α equal to 5%, then $Z_{0.05/2} = Z_{0.025} = 1.96$ (From Z table)

$Z_{\beta} =$ Assumed power of 80% $Z_{\beta} = 0.84$

$W =$ Willingness to pay threshold

$p =$ Expected correlation between difference in costs (ΔC) and effects (ΔQ)

$\Delta Q =$ Expected difference in mean effects

$\Delta C =$ Expected difference in mean costs

$Sd_Q =$ Expected standard deviation for the effects

$Sd_C =$ Expected standard deviation for the costs

To our knowledge, there is no published study has evaluated the direct and indirect costs and quality of life associated with mobile health app for the management of non-communicable diseases. Therefore, the calculation is based on the assumption and few literature results. According to a study published in Malaysia, RM 2499.15 is required for the managing of patient complicated with diabetes and heart failure after the first event (Shafie & Ng, 2020). The cost from the study is adjusted according to Consumer Price Index 2022. The cost difference between treatment group is considered as around 30% as reported by the use of mobile app in the management of heart failure study (Cano Martín et al., 2014). A minimum difference of 0.01 is estimated in term of QALY in favour of mobile health app user. Sd_c and Sd_Q are assumed as RM1000 and 0.01 respectively. The willingness to pay threshold is set at RM 28,470 per QALY as reported by Lim et al. (2017). The correlation coefficient is set at minimum 0.1 as estimated from cost-effectiveness analysis of a mobile-based intervention for patients with type 2 diabetes mellitus conducted by Li et al. (2021). A number of 150 patients (75 per study group) is required to detect at least 80% power assuming a two-tailed test and alpha of 5% between treatment group. The sample size will be rounded up to 200 patients to account for a possibility of 20% attrition. The sample size obtained is corresponding to the sample size applied in Li et al. (2021) cost-effectiveness analysis study.

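### No analysis of PDC on its percentage scale is named, so the refill-based primary measure is left to an adherent/non-adherent chi-square test that is probably less precise

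*Combined protocol and SAP*

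**What the plan says.** Section 4.4.1.1 measures the primary outcome, medication adherence, by MMAS-8 and by PDC from pharmacy refill records, at baseline, 3 months and 6 months. PDC is defined as a percentage, with one decision rule: "The patients are considered to be adherent if their PDC scores are ≥ 0.8 or 80" per cent. The section gives no equivalent cut-off for MMAS-8.

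Section 4.6 names three analyses for adherence:

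- MMAS: "Independent t-test or Mann-Whitney test will be used to compare MMAS score rankings" between the arms.
- MMAS again: ordinal logistic regression.
- Number of adherent patients: "Chi-Square test of independence will be used to determine the difference in number of patients with medication adherence between the intervention and control groups". Both follow-up times are tested. This sentence does not say which instrument defines adherence.

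Earlier in 4.6, a general sentence assigns the t-test to normally distributed or continuous variables and the Mann-Whitney test to non-normal data. PDC is not named anywhere in 4.6.

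Section 4.5 sizes the adherence outcome as a comparison of proportions: "Medication non-adherence rate of 50% is expected in control group and 40% is expected in intervention group". It concludes that "388 patients per arm should be recruited in the study" and, after 20% dropout, that "a minimum sample size of 970 is needed in this study, with the number of 485 in each arm". It then sets this figure aside as too large and settles on 200 patients, calculated from the cost-effectiveness outcome.

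**The concern.** A binary split at 80% treats unlike patients alike and like patients differently. At 6 months, patients with 40% and 75% of days covered both count as non-adherent, while patients with 79% and 81% fall on opposite sides. If the benefit is spread over the whole range of PDC, much of it never reaches the chi-square test.

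This matters more for PDC than for MMAS-8. Participants know their allocation (section 4.2) and MMAS-8 is a questionnaire, whereas PDC comes from refill records and is not self-reported. PDC is therefore the primary measure less open to reporting bias, and it is the one with no named full-scale analysis. The trial was also reduced from 970 to 200 patients, so precision on adherence is already scarce.

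There is a second stake. With no PDC test named or ranked, the choice between a continuous and a binary comparison could be made after the data are seen.

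**Working it through.** **Inputs from section 4.5.** Non-adherence is 50% against 40%, so adherence is 50% against 60%. The calculation is made "assuming a type I error of 5% and power of 80" per cent, with z = 1.96 and 0.84. The test is two-sided: 1.96 is used in both calculations, and the second is described as "assuming a two-tailed test and alpha of 5% between treatment group". Of 200 enrolled, 100 are in each arm; with 20% attrition, 100 × 0.80 = 80 per arm are evaluable.

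**Assumed, because the documents do not give it.** The SD and shape of PDC are assumed, as is the link between the 50% and 60% adherence rates and PDC ≥ 80%. Section 4.5 does not tie those rates to either instrument.

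**Step 1: reproduce the plan's figure.** With pooled P = 0.45, P(1 − P) = 0.2475 and 2(1.96 + 0.84)² = 15.68:

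n = 15.68 × 0.2475 / 0.10² = 388 per arm, and 388 / 0.80 = 485. Both agree with section 4.5.

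**Step 2: the same effect on the full scale.** If PDC, or a monotone transform of it, is normal with equal spread and the app shifts it, then going from 50% to 60% above a fixed cut is a shift of

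d = z(0.60) − z(0.50) = 0.2533 SD.

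n = 15.68 / 0.2533² ≈ 244.3, or 245 per arm rounded up. The ratio 388 / 244.3 ≈ 1.59 means that the binary test needs about 59% more patients for the same power. Equivalently, a split at the median keeps φ(0)² / (0.5 × 0.5) = 0.64 of the information. The share kept is 0.62 if 60% of patients lie above the cut and 0.49 if 20% or 80% do.

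**Step 3: power at the size actually planned.**

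- Full scale, 80 per arm: Φ(0.2533 × √40 − 1.96) = Φ(−0.358) = 0.36.
- Binary, 80 per arm: Φ(0.10 / √(2 × 0.2475 / 80) − 1.96) = Φ(−0.689) = 0.245. A slightly different variance formula gives 0.244.

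| Evaluable per arm | Binary (chi-square) | Full scale, d = 0.253 |
|---|---|---|
| 75 | 23% | 34% |
| 80 | 24–25% | 36% |
| 100 | 29% | 43% |

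**Step 4: sensitivity to shape.** PDC is bounded at 100% and probably skewed. Beta-shaped PDC was simulated with 50% and 60% of patients at or above 0.8, 80 per arm and 4,000 runs per setting. Chi-square power was 23–24%; t-test and Mann-Whitney power was 31–37%, with Mann-Whitney generally the higher of the two.

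**Step 5: the adverse case.** Suppose the app only moves some patients from below the 80% line to above it and otherwise leaves the distribution unchanged. Simulated power is then 23–24% for the binary test against 19–20% on the full scale, a loss of 3 to 5 points.

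**Step 6: baseline adjustment.** With correlation r between baseline and follow-up PDC, the required n is multiplied by (1 − r²). For assumed r of 0.3 to 0.5, this gives 223 to 184 per arm, and power of 39% to 46% at 80 per arm.

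**The case against.** A reader might infer that the plan definitely reduces PDC to a binary outcome and rules out any other analysis. The documents do not support that. The chi-square sentence names no instrument; the link to PDC is an inference, though a strong one, because the 80% rule is the only definition of adherent in the outcome section. The general t-test/Mann-Whitney sentence also covers a percentage such as PDC. What stands is narrower: no continuous PDC analysis is named, and none is ranked against the binary one.

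A reader might also infer that MMAS-8 loses information in the same way. It does not. MMAS is already given a t-test or Mann-Whitney test and an ordinal regression, and the phrase about rankings is loose wording rather than a loss of information.

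The size of the gain rests on an assumed distribution, and its direction reverses slightly if the app acts as a pure switch. This is a fair limit. The smooth shift seems the more plausible of the two, and the possible gain (about 11 to 12 points of power at 80 per arm under the normal model) exceeds the possible loss (3 to 5 points).

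Finally, the 80% cut-off is pre-specified, familiar, and consistent with a sample-size calculation based on proportions. That is a good reason to keep it as a reported result, but a weaker reason to let it be the only named test of PDC.

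**Conclusion.** The point holds as a gap in pre-specification with a likely cost in precision. Section 4.6 names no analysis of PDC as a percentage and leaves the refill-based primary measure most naturally to a chi-square test at the 80% cut.

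Under a smooth shift, the binary test is equivalent to giving up about 36–38% of the information near the planned rates. The result depends on the assumed shape of PDC and on reading the planned adherence rates as PDC ≥ 80%.

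It would be wrong to conclude that a continuous analysis rescues the trial. Power of about 36%, or up to about 46% with assumed baseline adjustment, remains far below 80%. The reduction from 970 to 200 patients is the larger problem and is not cured here. This is a cheap improvement that should be made, not a fatal defect.

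**What to change.** In section 4.6:

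- Name the between-arm difference in PDC (0–100%), with a 95% CI, as the main PDC analysis. Preferably adjust it for the baseline PDC that section 4.4.1.1 already provides for.
- Support it with a rank-based test, because PDC has a ceiling at 100%.
- Keep the proportion with PDC ≥ 80% and its chi-square test as a supportive result, and say explicitly that this is how adherence is defined for that test.

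Align sections 4.4.1.1 and 4.5 with this order, since the only adherence calculation in 4.5 is for a difference in proportions. In 4.5, state what the 200 patients can and cannot detect on the chosen scale, with the assumed PDC SD given openly.

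The cost is a change of text in three sections; no new data, visits or patients are needed. There are two downsides: a difference in percentage of days covered is a less familiar headline than per cent adherent, and a little power is lost if the app's effect is purely to carry patients across the threshold.
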